Subjects will be distributed equally into two groups. One group will receive active LFMS during the treatment week and the other group will receive sham LFMS during the treatment week. Treatment assignments will be randomized and balanced within blocks of 10. Randomization is performed automatically on the first treatment visit. The LFMS Device contains a pre-randomized folder of subject treatment links that are assigned to subjects as they arrive for their first treatment. This list was randomized in ten-subject blocks at the start of the study (using a random number generator). This randomization schedule has since been updated to reflect the parallel-group, 5-day design of this protocol.

V. STUDY PROCEDURES

Study Overview

b. Study visits and parameters to be measured (e.g., laboratory tests, x-rays, and other testing)

This study will consist of a screening visit; a baseline visit; we will aim to administer four or five daily LFMS treatment or sham treatment visits over a period of five days and one in-person follow-up visit for ratings on the Monday after the treatment week. If a subject is unable to attend only one treatment visit in the five day window, this will not be considered a protocol violation. Follow-up rating scales will be administered by phone once per week for two weeks following the last visit.

Visits and Procedures	Screening	Baseline	LFMS experimental treatment					Follow-Up Visit	Follow-Up Phone Call	Follow-Up Phone Call
	Visit 1	Visit 2	Visit 3	Visit 4	Visit 5	Visit 6	Visit 7	Visit 8		
LFMS			X	X	X	X	X			
M.I.N.I International Neuro-Psychiatric Interview (MINI)	X									
Cumulative Illness Rating Scale (CIRS-G)	X									
Mini-Mental State Exam	X									
Repeatable Battery for the Assessment of Neuropsychological Status (RBANS)		X						X		
LFMS Demographics Form	X									
LFMS Medical Screening Form	X									
LFMS Medications Form	X									
Drug Test	X									
Pregnancy Test	X		X	X	X	X	X			
Montgomery-Asberg Rating Scale (MADRS)	X	X	X		X		X	X	X	X
Hamilton Anxiety Rating Scale (HARS)		X	X		X		X	X	X	X
Positive and Negative Affect Schedule (PANAS)*		X	X	X	X	X	X	X	X	X
Young Mania Rating Scale (YMRS)	X	X	X	X	X	X	X	X	X	X

Low Field Magnetic Stimulation: Initial Trial in Geriatric Bipolar Depression

Columbia Suicide Severity Rating Scale (C-SSRS)	X	X	X	X	X	X	X	X	X	X

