During the screening visit, a trained clinical study staff member will interview and assess the subject using the Screening Measures, during which a detailed medical history will be obtained and current medications noted. Suicidality risk is assessed as part of the Safety Measures; a positive response to items 4 or 5 of the C-SSRS will prompt the use of the Suicidality SOP.

A urine drug screen and, if female, a pregnancy test will be performed. Subjects will be accepted for the treatment trial based on the interview and review of results by a study physician.

The screening visit, including the rating scales and physical exam, will take approximately 2 hours and will be done up to one week before the baseline visit. If subjects meet study criteria after the screening visit, a baseline visit will be scheduled.

Baseline (Visit 2) Procedures

Contingent on a successful screening visit, subjects will come in for a baseline visit on the Thursday or Friday prior to the 5 days of consecutive LFMS treatment. This visit will take about 1 hour to complete. Subjects will be administered Long- and Short-Term mood scales as well as the Safety Measures. A positive response to items 4 or 5 on the C-SSRS will prompt the use of the Suicidality SOP (see ‘Suicidality Procedures’ above).

LFMS (Visits 3-7) Procedures

Subjects will come in for 5 daily consecutive LFMS treatments over a period of five days, Monday-Friday. If subjects are unable to come in for five consecutive days due to a scheduling conflict, we will accept a schedule of four consecutive days without considering this a protocol deviation. Women of childbearing potential will be required to complete a urine pregnancy screen at screening and before each LFMS procedure.

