The Safety Measures will be administered. As part of these, the C-SSRS will be used as a suicidality risk assessment and any positive response to items 4 or 5 will prompt the use of the Suicidality SOP (see ‘Suicidality Procedures’ above). The second part of the Safety Measures is the CGI-I, which will be used to ensure safe continuation of the study; a score of 6 or more will prompt a consultation with the study physician and potential withdrawal from the study (see “Withdrawal Criteria” above). Medication and/or treatment changes will be asked about and noted. Changes in treatment will not prompt withdrawal but will indicate that data will be excluded from analysis (see “Medication and Therapy Change Procedures” above). A brief progress note will be recorded. The Short- and Long-Term mood scales will be

Low Field Magnetic Stimulation: Initial Trial in Geriatric Bipolar Depression

administered, and LFMS procedures will begin immediately after these mood ratings are completed. HARS and MADRS Long-Term mood scales will only be administered on Visits 3, 5, and 7.

Randomization occurs automatically when the subject number is entered on the LFMS Device during the first treatment visit.

For LFMS procedures, the subject will lie down on the patient table with his/her head positioned inside the device cylinder, and the operator will start the LFMS device. The device has been designed so that the cylinder does not extend below the eyes in order to reduce claustrophobia. Subjects will be instructed to remain silent during the treatment, except in cases of discomfort, desire to discontinue treatment, or similar situations related to subject safety and study participation. Subjects will be given one 20 minute exposure to either the LFMS or sham electromagnetic field treatment. Subjects will be told they may receive either the active treatment or a sham, inactive treatment.

After treatment, the Short-Term Measures will be completed again to obtain post-treatment scores. Subjects will also be asked about possible side effects or sensations. After the treatment and mood ratings, subjects may leave immediately or rest in the Imaging Center waiting area until they are ready to leave or return to the GPMADOC and the SAGE Program, located in South Belknap.

Follow-up Visit (Visit 8)

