The Monday following the set of 5 treatments (visits 3-7), subjects will meet with the study staff for a non-treatment follow-up visit. This visit will last up to 1 hour. During this visit, the Safety measures will be administered. As part of these, the C-SSRS will be used as a suicidality risk assessment and any positive response to items 4 or 5 will prompt the use of the Suicidality SOP (see ‘Suicidality Procedures’ above). Medication and/or treatment changes will be asked about and noted. Changes in treatment will not prompt withdrawal but will indicate that data will be excluded from analysis (see “Medication and Therapy Change Procedures” above).

The Long-term measures will be completed, as well as the PANAS. Subjects will be asked if they have experienced any change in their mood or noticed any effects. In addition, subjects will be asked whether they think they received active or sham LFMS.

Follow-up Phone Calls

In order to determine whether any effects are still felt after treatment stops, study staff will make one follow-up phone call each week on Monday for the 2 weeks after the Follow-up Visit. Short- and Long-Term Measures will be administered, and study staff will ask whether the subject has experienced any adverse side-effects. Safety Measures including the C-SSRS and the CGI-I will be administered, and a positive response to question 4 or 5 on the C-SSRS will trigger the Suicidality SOP.

k. Drugs to be used (dose, method, schedule of administration, dose modifications, toxicities), include Toxicity Grading Scale (if applicable)

N/A

l. Devices to be used

The LFMS Device is an electromagnetic coil situated on a cylinder with an inside diameter of 13.2 inches. It produces weak electromagnetic fields at a frequency of about 1000Hz; the magnetic fields are less than 30 Gauss and the electric fields are up to 1.43 V/m. A fully detailed description of the electromagnetic field distribution and waveform has been presented in the IDE submission to the FDA (and determined to be a non-significant risk device).

m. Procedures/surgical interventions, etc.

N/A

n. Data to be collected and when the data is to be collected

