During the treatment visits, research data will be obtained through mood rating scales before and after the LFMS procedures, and through self-report from the subjects. Research data will also be obtained from subjects through mood rating scales at the follow-up visits, one week after the start of the set of 5 experimental LFMS procedures.

VI. BIOSTATISTICAL ANALYSIS

d. Specific data variables being collected for the study (e.g., data collection sheets).

The primary long-term measures will be the change in MADRS and HARS scores at one week compared to baseline across the treatment week. This analysis will be a repeated measures ANOVA with a baseline covariate. The primary short-term analyses using the PANAS scores, which provide additional insight into the details of mood change, will be performed in the same way.

e. Study endpoints

The main endpoint of this study is that participants will well tolerate 5 daily active treatments. A secondary endpoint is the expectation that participants will experience a persistent increase in positive mood at one week after the start of treatment. Change in mood over the first treatment is an additional measure that will ensure comparability of the study to previous studies.

f. Statistical methods and Power analysis

This is an exploratory study being performed to characterize the effects of LFMS over daily treatments and at one week in a target population. As the endpoints are safety and tolerance by the participants, no power analysis has been performed. We expect to be able to make the first estimate of an effect size based on the results of this study.

VII. RISKS AND DISCOMFORTS (Stratify by common and uncommon)

d. Complications of surgical and non-surgical procedures, etc.

Risks Related to Confidentiality and Privacy

There is a risk that a breach of privacy or confidentiality could occur. But, all study staff are trained in how to preserve confidentiality and privacy. Risks will be minimized by storing subject data and personal information on a password protected computer or in a locked filing cabinet in a locked office, accessible only to study staff.

Psychosocial (non-medical) risks

There is a risk that questions during the treatment visits about mental health and mood state may upset the subject psychologically. Subjects are free to take a break from or to stop answering these questions at any time, and a study physician will be able to assist them if needed.

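### Phase 2 MADRS and HARS: naming the visits and using both pre-LFMS ratings as baseline in a mixed model is a cheap improvement to the efficacy estimate

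*Combined protocol and SAP*

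**What the plan says.** All references are to the Phase 2 part of the combined protocol and SAP.

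- **Analysis (VI.d).** The long-term measures, changes on the MADRS and the HARS, are described in these words: "scores at one week compared to baseline across the treatment week. This analysis will be a repeated measures ANOVA with a baseline covariate". The next sentence sends PANAS to the same analysis.
- **One-week time point (V.n; Follow-up Visit).** Follow-up ratings fall "one week after the start of the set of 5 experimental LFMS procedures". The visit is described as: "The Monday following the set of 5 treatments (visits 3-7), subjects will meet with the study staff for a non-treatment follow-up visit". One week is therefore Visit 8.
- **First pre-treatment rating (Baseline, Visit 2).** "subjects will come in for a baseline visit on the Thursday or Friday prior to the 5 days of consecutive LFMS treatment". The schedule marks both scales here.
- **Second pre-treatment rating (LFMS, Visits 3-7).** In treatment week both scales are rated only at Visits 3, 5 and 7, and "LFMS procedures will begin immediately after these mood ratings are completed". Randomization takes place at the device on the first treatment visit.
- **Attendance.** The treatment section says "Subjects will come in for 5 daily consecutive LFMS treatments over a period of five days, Monday-Friday", and for a scheduling conflict "we will accept a schedule of four consecutive days without considering this a protocol deviation". The Study Overview says "If a subject is unable to attend only one treatment visit in the five day window, this will not be considered a protocol violation".
- **Size and purpose.** The target is 32 completers in two equal groups. VI.f calls the study exploratory, gives no power analysis, and expects it to yield a first effect-size estimate.

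**The concern.** The one-week time point and the active-versus-sham contrast can be inferred. Three other things cannot: the covariate visit, the list of repeated visits, and what happens when a rating is missing.

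The most natural covariate is Visit 2, because its column is headed Baseline. On that reading the Visit 3 score, already collected before exposure, is not used as a baseline. If Visit 3 enters instead as one of the treatment-week levels, a visit with no possible treatment effect is averaged into the group comparison. And because a permitted missed session can fall on a rating day, the handling of missing ratings decides whether that subject's Visit 8 score counts.

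What is at stake is the precision of the first effect-size estimate in about 32 people, not tolerability.

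**Working it through.** **Inputs.** From the documents: 32 completers, taken as 16 per arm; Visit 2 is 3-4 days before a Monday Visit 3; Visit 8 is 7 days after Visit 3. Assumed: SD 8 points, all correlations, and an 0.8 SD effect in step 3. The plan gives no power or precision figure to reproduce.

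**1. Equal correlation ρ between visits.** Visit 8 residual variance as a share of SD²: one baseline 1 − ρ²; mean of two baselines 1 − 2ρ²/(1 + ρ). The 95% CI half-width is 8 × √(share × 2/16) × 2.045 (t on 29 df).

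| ρ | One baseline | Mean of two | Cut | Half-width |
|---|---|---|---|---|
| 0.3 | 0.910 | 0.862 | 5.3% | 5.52 to 5.37 |
| 0.5 | 0.750 | 0.667 | 11.1% | 5.01 to 4.72 |
| 0.7 | 0.510 | 0.424 | 17.0% | 4.13 to 3.76 |

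**2. Serial decay with measurement error.** Correlation = w × r^(days/7), with weekly r from 0.5 to 0.9, reliability w from 0.7 to 1.0, and a 3.5-day gap between Visits 2 and 3. Write r23, r38 and r28 for the pairwise correlations. Residual variance with the mean is 1 − (r28 + r38)²/[2(1 + r23)]; with Visit 2 alone, 1 − r28²; with Visit 3 alone, 1 − r38².

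- r = 0.5, w = 0.7: r23 = 0.495, r38 = 0.350, r28 = 0.247. Visit 2 alone 0.939, mean 0.881: a 6% cut.
- r = 0.9, w = 1.0: r23 = 0.949, r38 = 0.900, r28 = 0.854. Visit 2 alone 0.271, mean 0.211: a 22% cut. Visit 3 alone is 0.190, so the mean is 11% worse than that.
- r = 0.9, w = 0.7: r23 = 0.664, r38 = 0.630, r28 = 0.598. Visit 3 alone 0.603, mean 0.547: the mean is 9% better.

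Against Visit 2 alone the cut is about 6-22%. Against Visit 3 alone the result runs from about 9% lower to 11% higher variance. Under the equal correlation of step 1, either single visit gives the same 5-17% cut.

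**3. Visit 3 as an outcome level.** Suppose the effect is constant at Visits 5, 7 and 8 and zero at Visit 3. The group main effect over four levels is then 3/4 of the true effect, so 0.8 SD becomes 0.6 SD. With all correlations 0.6 and 16 per arm, power for that main effect is about 79%. It is 94% if Visit 3 is left out and 98% if it is averaged into baseline. A contrast taken at Visit 8 alone is not diluted.

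**4. Permitted missed session.** Take outcomes at Visits 5, 7 and 8, with visit numbers fixed to Monday-Friday. Under the Study Overview any one of five sessions may be missed, and two of those (Visits 5 and 7) remove an outcome: 2 of 5. Under the four-consecutive-days rule the missed day is Monday or Friday, and only Friday (Visit 7) removes one: 1 of 2. If visits are numbered in sequence, a subject with four sessions has no Visit 7 in any pattern.

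For illustration, assume 8 of 32 subjects miss a session, with patterns equally likely. A complete-case analysis over those three visits then loses 8 × 0.4 = 3.2, 8 × 0.5 = 4, or 8 subjects. The half-width ratio √(32/n) × t(n−3)/t(29) is 1.06, 1.08 or 1.17. An analysis of Visit 8 alone loses nobody for this reason.

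**The case against.** A reader might infer that the plan discards the Visit 3 rating. The documents do not show this: VI.d names no covariate visit and speaks of the treatment week, so Visit 3 may already be in the model in some role. The one-week clock runs from the first treatment, which makes Visit 3 a possible intended baseline. If so, averaging in Visit 2 gains little or nothing under decay. This part of the objection stands and limits the claimed benefit.

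A reader might also infer that subjects who kept to the protocol will be dropped, widening the interval by 6-17%. That needs complete-case handling, a particular set of outcome visits, a numbering rule and 8 missed sessions. VI.d neither states nor rules out the first two, the numbering is not given, and the 8 is assumed. The widening illustrates a risk and is not a property of the plan.

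It is also fair to say that the gain is modest, that every correlation is assumed, and that the study is exploratory with tolerability as its main endpoint. That supports a low severity. It does not remove the case for naming the visits and using ratings already collected. With complete data the mixed model would give essentially the same visit contrast as the ANOVA, so its own benefit is confined to missing ratings.

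**Conclusion.** This holds as a cheap improvement to the efficacy estimate. Two pre-exposure ratings of each scale are scheduled, and the analysis sentence fixes neither the baseline visit nor the outcome visits. Against a Visit 2 covariate, the mean of the two lowers Visit 8 residual variance in every scenario examined, by roughly 5% to 22%. Against Visit 3 alone it is about neutral under decay. The sizes rest wholly on assumed correlations; the direction against Visit 2 does not depend on the assumed SD. Stating that Visit 3 is not an outcome removes a possible dilution, and a mixed model keeps the available ratings of subjects who miss a visit. Excluding the data of subjects whose medication or therapy changes is a separate matter that this does not address.

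**What to change.** In VI.d, replace the ANOVA sentence for MADRS and HARS with:

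> MADRS and HARS will each be analysed with a mixed model for repeated measures with outcomes at Visits 5, 7 and 8. Fixed effects are arm, visit, arm-by-visit and baseline, where baseline is the mean of the available pre-LFMS ratings at Visits 2 and 3. Visit 3 is not an outcome. Subjects with a missing visit rating are included. Covariance is unstructured, with compound symmetry if it does not converge, and Kenward-Roger degrees of freedom are used. The main efficacy estimate is active minus sham at Visit 8 with its 95% CI.

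Give PANAS its own analysis sentence. It is rated at every treatment visit, before and after LFMS, so the present cross-reference would no longer fit.

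Separately, reconcile the Study Overview with the LFMS (Visits 3-7) section on which single missed sessions are accepted, and state how visits are then numbered.

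**Cost.** Wording only; no visit or rating is added. The mixed model needs the stated small-sample correction and covariance fallback in about 32 subjects (unstructured over three visits has 6 parameters). Averaging may bring little or no gain if Visit 3 alone was the intended baseline.

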- Hypothesis 2: We hypothesize that subjects will show long-term improvement over one week in anxiety following the first LFMS experimental treatment, as measured by the Hamilton Anxiety Rating Scale (HARS).

Aim 3: To assess any cognitive benefits from regular LFMS in older adults suffering from bipolar depression.

Low Field Magnetic Stimulation: Initial Trial in Geriatric Bipolar Depression

- Hypothesis 3: We hypothesize that subjects will show cognitive improvement, as measured by the Repeatable Battery for the Assessment of Neuropsychological Status (RBANS), at the follow-up visit as compared to baseline.

III. SUBJECT SELECTION

Up to 64 subjects will be enrolled in order to achieve our target of 32 completers of the treatment protocol. Subjects will be referred by clinicians from the Division of Geriatric Psychiatry at McLean Hospital.

d. Inclusion/Exclusion criteria

Inclusion criteria:

6. Subjects will be men or women aged 55 years or older.
7. Subjects will have a diagnosis of Bipolar Disorder Type I or II, current episode depressed as measured by a MADRS ≥ 20 .
8. Subjects must be maintained on a stable dose of all psychotropic medications for a period of at least two weeks prior to screening.
9. Subjects must be capable of providing informed consent.
10. Subjects must live within 2 hours of McLean Hospital.
11. Subjects must have a treating psychiatrist within 2 hours of McLean Hospital.

Exclusion criteria:

8. Dangerous or active suicidal ideation.
9. Subjects meeting DSM-V criteria for any Axis I disorder other than Bipolar Disorder or an anxiety disorder (e.g. Major Depressive Disorder, dementia).
10. Subject has an MMSE score ≤ 24 .
11. Subject is pregnant or plans on becoming pregnant.
12. Subject has recent history (within 7 days of screening) of ECT or TMS treatment.
13. Subject has recent history of substance abuse (cannot meet DSM-V criteria for substance abuse, no significant drug abuse within last 3 months, no history of dependence in last year, no drug use within last month, other than marijuana use).
14. Subject is experiencing active psychosis as determined by “yes” answers to questions K12 and K13 in the Mini International Neuropsychiatric Interview (MINI).
15. Subject has any contraindication for MRI (i.e. Presence of a pacemaker, neurostimulator, or metal in head or neck).

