For safety purposes, use of the LFMS device follows standard MRI procedures. The LFMS device is assessed by the McLean Hospital Biomedical Engineering department annually to ensure the device operates within safe parameters.

e. Withdrawal Criteria:

Participation in this research study is voluntary. Subjects will be informed that they may withdraw from this study at any time. Subjects also will be informed that study staff may terminate participation at any time if they feel that it is in the best interest of the subject or study.

Objective criteria for removing a subject from the study include: if they become no longer eligible for the study between screening and treatment per inclusion/exclusion criteria (e.g. drug use or pregnancy), if they have dangerous or active suicidal ideation at any time during the study (as determined by C-SSRS and suicide related questions on the MADRS and the opinion of a study clinician), or if their CGI-I score, determined as part of the Safety Measures, shows a change of ≥ 8 , or if any intolerable discomfort from the study procedures occurs.

f. Source of subjects and recruitment methods

Study subjects will be recruited via clinician referrals from the Geriatric Psychiatry Mood and Anxiety Disorders Outpatient Clinic (GPMADOC) and the SAGE Program, located in South Belknap. Clinicians associated with these

Low Field Magnetic Stimulation: Initial Trial in Geriatric Bipolar Depression

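### Phase 2 main endpoint names five active sessions, but the schedule accepts four and the endpoint leaves out the randomised sham arm

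*Combined protocol and SAP*

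**What the plan says.** All references are to the Phase 2 protocol dated September 17, 2018.

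- **Endpoint (VI.e, Study endpoints).** "The main endpoint of this study is that participants will well tolerate 5 daily active treatments". Good tolerance is not defined, and no denominator, threshold or method of analysis is given. The repeated measures ANOVA in VI.d is assigned to MADRS, HARS and PANAS. VI.f gives safety and tolerance as the reason for having no power analysis.
- **Schedule (V.b, Study Overview).** "we will aim to administer four or five daily LFMS treatment or sham treatment visits over a period of five days". On a missed session: "If a subject is unable to attend only one treatment visit in the five day window, this will not be considered a protocol violation".
- **Schedule (LFMS Visits 3-7 Procedures).** The default is five daily sessions, Monday to Friday. For a scheduling conflict, "we will accept a schedule of four consecutive days without considering this a protocol deviation".
- **Allocation (IV.f).** "Subjects will be distributed equally into two groups", one active and one sham. "Randomization is performed automatically on the first treatment visit".
- **Recruitment (III).** "Up to 64 subjects will be enrolled in order to achieve our target of 32 completers of the treatment protocol". Whether a four-session subject is a completer is not stated.
- **Removal (III.e, Withdrawal Criteria).** The grounds end with "or if any intolerable discomfort from the study procedures occurs".
- **Exclusion of data (V.i, Medication or Therapy Changes).** Data from subjects whose medication or therapy changes are left out of analyses. Nothing says whether this reaches the tolerability endpoint.
- **Tolerability data.** The visit table has an adverse-event check-in at each treatment visit. Side effects and sensations are asked about after each session. IX.d lists device completion status and side-effect notes among the records.

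**The concern.** The endpoint and the schedule count different things. A subject who attends four sessions because of a diary conflict has complied with the protocol and may have had no discomfort, yet has not tolerated five sessions. No rule says how to score that subject.

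The endpoint also refers to active treatment only. Early stopping and reported sensations can arise from daily travel, lying in the device or expectation. The sham arm is what separates these from an effect of the field, and the endpoint does not use it.

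With no stated denominator, the same data can yield quite different headline rates, and the choice could be made after the results are known. This matters because tolerance is both the main endpoint and the stated reason for having no power analysis.

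**Working it through.** The plan gives no tolerability rate, dropout rate, alpha or power, so there is no figure of its own to reproduce beyond the recruitment ratio, 32/64 = 50%.

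**Inputs**
- Target of 32 completers from up to 64 enrolled (section III).
- Equal allocation (IV.f). Assuming equal completion in the two arms, active completers = 32/2 = 16. This is an assumption: with blocks of 10, the first 32 randomised are three full blocks (15 active) plus two more, giving 15 to 17 active.
- Number of compliant four-session subjects, k: not in the documents, so shown as a range.

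**1. Literal five-session count.** Suppose all 16 active subjects comply and tolerate every session they attend, and k of them attend four. The rate is (16 − k)/16, so each such subject costs 1/16 = 6.25 points.

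| k | Rate | Exact (Clopper-Pearson) 95% CI |
|---|---|---|
| 0 | 16/16 = 100% | 79.4% to 100% |
| 1 | 15/16 = 93.8% | 69.8% to 99.8% |
| 2 | 14/16 = 87.5% | 61.7% to 98.4% |
| 4 | 12/16 = 75.0% | 47.6% to 92.7% |

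If each subject independently has probability q of taking four sessions, the chance of at least one among 16 is 1 − (1 − q)^16. For assumed q of 5%, 10% and 20% this is 56%, 81% and 97%. The mismatch is therefore likely to arise even if missed sessions are uncommon.

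**2. Completers as denominator.** Subjects removed for intolerable discomfort are not completers, so this denominator drops the least tolerant and biases the rate upward. Two cases:
- Tolerance taken to mean completion, with four-session subjects counted as completers: 16/16 = 100% (79.4% to 100%), whatever the attrition.
- Tolerance judged on side effects: (16 − m)/16 with m poor tolerators. For m = 2 this is 14/16 = 87.5%.

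**3. All randomised to active and treated as denominator.** Suppose 20 are treated and 16 complete. Completion is 16/20 = 80% (56.3% to 94.3%). If only stopping for discomfort or an adverse event counts as failure, the rate lies between 16/20 = 80% (all four left for that reason) and 20/20 = 100% (none did). The reason for leaving decides the result, so it has to be recorded. The extreme for completion is 16/32 = 50% (31.9% to 68.1%), which needs all 64 enrolled to be randomised. Since randomisation happens at the first treatment visit, some of the 64 may be screen failures.

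**4. The two schedule statements.** The overview excuses any one missed visit. The treatment-visit section accepts four consecutive days. A subject who misses only the Wednesday meets the first and not the second. The passages must be reconciled before any per-schedule count is possible.

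**The case against.** The best defence is that VI.e is not a responder definition. It can be read as naming the regimen, with four sessions as an attendance allowance, and the study calls itself exploratory with no decision rule attached to this endpoint. On that view this is a wording mismatch and not a demonstrated bias in a planned estimate. That is fair as to size: the literal count is one reading, and the number of four-session subjects is unknown. It does not remove the mismatch, because nothing in the plan says which reading applies.

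A second defence is that sham subjects have the same visits and the same adverse-event questions, so a sham rate will be available. That also stands, and it makes the remedy cheap. The endpoint as written still does not call for the comparison.

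A reader might go further and infer that the tolerability rate is 100% by construction because recruitment aims at completers. The documents do not support this. The 32 is a recruitment target and not an analysis set. Side effects and adverse events are collected separately from completion, so a completer can score as a poor tolerator. Nor is it stated that a four-session subject is a completer.

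A reader might also infer that subjects who stop are replaced until 32 finish. Enrolment is capped at 64, no replacement procedure is described, and part of the gap between 64 and 32 may be screen failures.

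**Conclusion.** The point holds for the five-versus-four mismatch, the missing denominator and the unused sham arm. On a literal reading, each compliant four-session subject who tolerated treatment lowers the active rate by 6.25 points, given 16 active subjects (equal completion by arm assumed). The range shown, 93.8% to 75% for one to four such subjects, is illustrative and not a forecast.

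A completers-only count would be biased upward by removal for intolerable discomfort. It would equal 100% only under two further conventions that the protocol does not adopt: tolerance means completion, and four sessions count as completion. The flaw should be corrected, but for an exploratory study with no decision rule on this endpoint it does not undermine the design.

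**What to change.** 1. Reconcile VI.e with the four-or-five-session schedule, and reconcile the two schedule statements with each other.
2. Define the endpoint as the proportion of all randomised subjects with at least one session who neither stop nor are withdrawn because of discomfort or an adverse event. Sessions missed for scheduling or other unrelated reasons are then not failures.
3. Keep withdrawn subjects in the denominator, and state that the data exclusion for medication or therapy changes does not apply to this endpoint.
4. Report the rate for active and sham separately with exact 95% intervals, and give the active-sham difference.
5. Report side effects and adverse events by arm alongside it, so that a subject who finishes with marked side effects remains visible.
6. Record the reason for every missed session and every withdrawal. The data items listed in IX.d do not include it.

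The cost is a change of wording and slightly more recording. Session completion and side-effect notes are already planned. The resulting rate may look less favourable than one counted among completers.
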